10.4.6 Baseline Descriptive Statistics

Patient baseline characteristics will be tabulated for both SSU and usual care groups. Specifically, means (standard deviations) or medians (interquartile range) will be presented for continuous variables such as age and body mass index. For categorical variables, such as gender and race, frequency and percentages will be presented. Group comparisons of continuous variables will be based on either two-sample t-tests (under normality) or Wilcoxon's Rank Sum test. Normality of distribution will be determined using the Kolmogorov-Smirnov goodness-of-fit test. Categorical data comparisons will be presented based on the Chi-square or Fisher's exact test. Standardized difference is used to compare the mean of the SSU and usual care groups.⁷²

10.4.7 PLANNED INTERIM ANALYSES

Formal interim analysis will occur after 50% of patients have been accrued. No formal stopping rules have been established, given the clinical effectiveness study design. In other words, safety concerns are unlikely and equivalent outcomes would not be defined as futile. Rather, the DSMB will issue recommendations on halting the trial early, only for safety reasons, based on the totality of data reviewed.

10.5 SAMPLE SIZE

A one-day difference in the length of hospital stay is a 20% reduction in the mean length of stay(LOS) of five days during hospitalization (median LOS =4.3 days).⁵⁰ Pilot data support the clinical significance of a one-day reduction,⁴⁵ and discussions with patients and caregivers confirms this finding. *While we anticipate achieving greater than a one-day difference, we have powered our study conservatively.*

$$N (\text{total}) = 534; \quad N_1 = 267; \quad N_2 = 267$$

Based on published data,⁴⁶ we project that DAOOH has a mean of 25.6 with a standard deviation of 3.9 in the control arm. A reduction of the mean DAOOH by one-day is the minimal clinically meaningful difference as determined through our patient engagement outreach.⁵⁴ An interim analysis when half of the outcome data are available will be performed. (See DSMB, section E6). Accounting for this with the O'Brien-Fleming spending function, 240 subjects per arm are required to achieve 80% power in detecting the one-day difference in DAOOH, where the two-sided type I error rate is controlled at 0.05. Assuming 10% attrition due to drop-outs and lost to follow up, this study requires a total of 534 subjects. This power calculation also takes into account a conservative estimate of 40% of patients being admitted to the hospital from the SSU arm. *DAOOH automatically accounts for death.* The maximal number of days alive and out of the hospital through 30 days post randomization is 30 days. If a patient were to die on day 8 post-randomization, her DAOOH would be 8. This would be compared to a patient who stayed in the hospital 3 days after randomization, but never returned to the ED or hospital or died through 30 days. DAOOH of this patient would be 27. If the same patient returned to the hospital on day 12 for 2 days, and again on day 24 for 2 days, their total DAOOH would be 23.

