2.2 RATIONALE

Small studies, retrospective analyses, and the Society for Cardiovascular Patient Care (SCPC; now American College of Cardiology [ACC] Accreditation Services) guidelines support brief observation (< 24 hours) or short stay unit (SSU) management of AHF to be effective for lower risk AHF patients. Our group's early work demonstrated lower overall median length-of-stay compared to a risk-matched inpatient only group (25.7 vs 58.5 hours).⁴⁵ Importantly, total charges were approximately \$3600 less for the SSU compared with those admitted from the ED. In a retrospective study of 358 patients using SCPC guidelines, the authors observed less hospital bed day utilization and similar 30-day readmission rates (12.5% vs 10.0%), respectively after adjustment for age, race, sex, BNP, renal function and ejection fraction.⁴⁶ SSU discharges spent 2.4 days and 2.5 days within 30 and 90 days of follow-up, respectively, compared with 4.4 and 5.0 days among patients admitted to the hospital after SSU management ($p<0.0001$).⁴⁶ Those patients who weren't ready for discharge after SSU management were admitted to the hospital for further treatment. **However, several knowledge gaps hinder broad uptake of SSU management.** First, an adequately powered, randomized controlled trial of SSU AHF care has not yet been conducted. Second, the impact of a SSU AHF strategy on quality of life and caregiver burden is unknown. Third, due to reimbursement differences, patients may face increased out-of-pocket costs. Finally, clinicians and caregivers may think SSU is just 'gaming the system' to avoid readmission penalties. We address each of these gaps in our proposal.

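### The planning mean for days alive and out of hospital appears to deduct bed-days only; if the SD of 3.9 also leaves out deaths, the stated 80% power for a one-day difference is too high

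*Combined protocol and SAP*

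**What the plan says.** Section 10.5 takes its planning values from a published study (reference 46): "we project that DAOOH has a mean of 25.6 with a standard deviation of 3.9 in the control arm". From these it concludes that "240 subjects per arm are required to achieve 80% power in detecting the one-day difference in DAOOH", at a two-sided 5% level with one interim look under an O'Brien-Fleming spending function. It then adds 10% for attrition to reach 534.

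The same section says that "DAOOH automatically accounts for death". Its worked example gives a patient who dies on day 8 a score of 8. Section 10.1.1 adds that death is the most heavily weighted part of the endpoint. Section 10.4.2 (capture of the endpoint) says that all time in the ED, SSU or inpatient ward is deducted.

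Section 2.2 describes reference 46 as a retrospective study of 358 patients. It reports 2.4 hospital days within 30 days for patients discharged from the SSU, "compared with 4.4 and 5.0 days among patients admitted to the hospital after SSU management"; the first of those two figures is the 30-day one.

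Section 10.5 also justifies the target difference with a figure from another source (reference 50): "A one-day difference in the length of hospital stay is a 20% reduction in the mean length of stay(LOS) of five days".

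**The concern.** The planning mean equals 30 minus the 4.4 bed-days from the same reference, to the decimal. That leaves almost no room for days lost to death. The mean and SD are given as a pair for one variable from one source, so the natural reading is that 3.9 is the SD of bed-days.

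The endpoint to be analysed is different. A patient who dies early scores far below the rest, so even a few deaths widen the SD. The sample size depends only on the one-day difference and the SD, and 240 per arm is the bare requirement for 80%, so nothing is in reserve. If the SD leaves deaths out, the trial is less able to detect one day than the plan says, and a null result could be given more weight than it deserves.

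There is also a question about the source group. Section 10.5 labels the figures as control arm, but section 2.2 attaches the 4.4 days to patients admitted after SSU management. Controls in this trial are admitted without SSU care (section 6.1.1).

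**Working it through.** **1. The plan's own figure.** Inputs from section 10.5: difference 1 day, SD 3.9, two-sided 5%, 80% power.

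- Fixed design: n per arm = 2 × (1.960 + 0.842)² × 3.9² / 1² = 238.8, so 239.
- With one look at 50% under O'Brien-Fleming spending, the final critical value is 1.979 and the inflation factor 1.0087, giving 240.8 per arm.
- Power at 240 per arm: 80.0% (two-sample t, fixed design), or 79.9% by normal approximation with the interim look.
- Attrition: 240 / 0.9 = 266.7, so 267 per arm and 534 in total.

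The stated design reproduces from its stated inputs.

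**2. Where 25.6 comes from.** 30 - 4.4 = 25.6. Each figure is rounded to one decimal, so the two could hide a gap of at most about 0.1 day. Under the model in step 3, each 1% of mortality lowers the mean by 0.11 to 0.15 day. The match therefore leaves room for mortality of no more than about 1%.

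**3. What deaths would do to the SD.** Assumptions, none of them given in the documents:

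- survivors have mean 25.6 and SD 3.9;
- a fraction p dies, at times uniform over 30 days;
- both arms share the SD, and the overall difference stays at one day.

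With M and V the mean and variance of the score among those who die:

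Variance = (1 - p) × 3.9² + p × V + p(1 - p) × (25.6 - M)²

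- Rule A, score equals day of death (the example in section 10.5): M = 15, V = 30²/12 = 75.
- Rule B, 4.4 hospital days also deducted, floored at zero (in line with section 10.4.2): M = 25.6²/60 = 10.92, V = 25.6³/90 - 10.92² = 67.1.

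Example at p = 2%:

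- Rule A: 14.91 + 1.50 + 2.20 = 18.61, so SD 4.31.
- Rule B: 14.91 + 1.34 + 4.22 = 20.47, so SD 4.52.

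**4. Power for one day at 240 per arm** (two-sample t; in these scenarios the interim look costs less than half a point more):

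| Assumed 30-day mortality | SD, rule A | Power, rule A | SD, rule B | Power, rule B |
|---|---|---|---|---|
| 0% | 3.90 | 80% | 3.90 | 80% |
| 0.5% | 4.01 | 78% | 4.07 | 77% |
| 1% | 4.11 | 76% | 4.23 | 73% |
| 2% | 4.31 | 72% | 4.52 | 68% |
| 3% | 4.50 | 68% | 4.80 | 62% |
| 4% | 4.68 | 65% | 5.06 | 58% |

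If 3.9 already includes deaths, the first row applies whatever the mortality.

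**The case against.** The strongest objection is that the mean has no bearing on power. The match at 25.6 says how the mean was built; it does not prove how the SD was built. The documents do not derive 3.9, and the cited study is not available to check. This stands, and it is why the power loss is stated conditionally. A reader might infer that the sample size arithmetic is wrong or that power is certainly below 80%. The documents support neither: the arithmetic reproduces, and the shortfall depends on an SD whose content is not stated.

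A reader might also take the five-day mean stay as capping control DAOOH at 25.0, which would make 25.6 impossible. It does not. Five days comes from a different study, of acute heart failure in US emergency departments generally, while this trial enrols lower-risk patients. Section 2.2 itself quotes a median of 58.5 hours for a risk-matched inpatient group. The two figures need explaining, but neither affects power.

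The plan also expects more than one day. With the 40% admission rate from the SSU that it allows for, the section 2.2 figures give 0.6 × 2.4 + 0.4 × 4.4 = 3.2 days against 4.4, a difference of 1.2. At 1.2 days, power stays at about 80% or above through 4% mortality under rule A, and through 2% under rule B. That softens the practical consequence. It does not rescue the stated claim, which is 80% power for one day.

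Finally, the description of the source group is the protocol's own paraphrase in section 2.2, and it may be that paraphrase, not section 10.5, that is wrong. Hence the two need reconciling; the documents do not show which is in error.

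**Conclusion.** The point holds in conditional form. The planning mean appears to be 30 minus bed-days, with at most about 1% mortality hidden by rounding, for an endpoint that weights death most heavily. The SD is presented as belonging to that same variable. If it too excludes deaths, the 80% is overstated by about 2 to 3 points at 0.5% mortality and by 15 to 22 points at 4%. The width of each range reflects the two scoring rules that the protocol's own text allows. The results rest on assumed mortality, uniform death times and a difference held at one day.

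A reader might go further and conclude that enrolment must rise. Under rule A, with the interim look and 10% attrition, restoring 80% would take about 596 patients in total at 1% mortality and 716 at 3%. The documents do not establish the condition behind those totals, so they do not support a larger trial on this ground. They do show that a single power figure is more certain than its inputs allow.

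**What to change.** In section 10.5:

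1. Restate power for a one-day difference at 240 per arm as a range over 0 to 4% 30-day mortality, under both scoring rules, with mortality labelled as an assumption. Say which scoring rule the analysis will use.
2. State whether the SD of 3.9 includes deaths, and which patients it describes.
3. Reconcile the control-arm label with the description of the 4.4-day group in section 2.2, and explain how 25.6 sits beside the five-day mean stay.

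Optionally, compute the SD pooled over both arms, not split by arm, at the 50% look already planned in section 10.4.7, and compare it with 3.9.

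The cost is a few sentences and a less favourable stated power. No change to enrolment, design or the analysis method is proposed.

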10.6 MEASURES TO MINIMIZE BIAS

10.6.1 ENROLLMENT/ RANDOMIZATION/ MASKING PROCEDURES

Patients will be randomized 1:1 to one of the two study arms, but stratified by site to ensure equal site representation. A central computer generated randomization scheme with random block sizes of two, four, and six will be created, stratified by site. The REDCap randomization module will be utilized to generate the randomization schema and patient allocation.

Due the nature of the intervention and the clinical setting, this is an unblinded trial.

11 SOURCE DOCUMENTS AND ACCESS TO SOURCE DATA/DOCUMENTS

The medical experts, study monitors, auditors, and health authority inspectors (or their agents) will be given direct access to source data and documentation (e.g., medical charts/records, laboratory test results, printouts, videotapes) for source data verification, provided that patient confidentiality is maintained in accordance with local requirements.

Each Investigator must maintain, at all times, the primary records (i.e., source documents) of each patient's data. Examples of source documents are hospital records, office visit records; examining physician's finding or notes, consultant's written opinion or notes, laboratory reports, drug inventory, study drug label records, and CRFs that are used as the source.

Each Investigator will maintain a confidential patient identification list that allows the unambiguous identification of each patient. All study-related documents must be kept for a minimum of 5 years. A publicly available dataset will be released per NIH guidelines.

12 QUALITY ASSURANCE AND QUALITY CONTROL

Protocol Amendments: No changes from the final approved (signed) protocol will be initiated without the prior written approval or favorable opinion of a written amendment by the IEC/IRB, except when necessary to eliminate immediate safety concerns to the patients or when the change involves only logistics or administration. Each Investigator will sign the protocol amendment.

The IRB/EC may provide expedited review and approval/favorable opinion for minor change(s) in ongoing studies.

Protocol Deviations, Violations, and Exceptions: A **protocol deviation** is non-adherence to protocol-specific study procedures or schedules that does not involve inclusion/exclusion criteria, primary objective variable criteria, and/or GCP guidelines. Deviations are considered minor and do not impact the study.

A **protocol violation** is any significant divergence from the protocol, i.e., non-adherence on the part of the patient, the Investigator, or the sponsor to protocol-specific inclusion/exclusion criteria, primary objective variable criteria, and/or GCP guidelines. Protocol violations will be identified and recorded, by study center personnel.

No **exceptions** to protocol-specific entry criteria will be granted to allow patients to enter a study.

Information to Study Personnel: Each Investigator is responsible for giving information about the study to all staff members involved in the study or in any element of patient management, both before starting the practical performance of the study and during the course of the study (e.g., when new staff become involved). Each Investigator must assure that all study staff members are qualified by education, experience, and training to perform their specific responsibilities. These study staff members must be listed on the study center authorization form, (if required) which includes a clear description of each staff member's responsibilities. This list must be updated throughout the study, as necessary.

The study monitor is responsible for explaining the protocol to all study staff, including each Investigator, and for ensuring their compliance with the protocol. Additional information will be made available during the study when new staff become involved in the study and as otherwise agreed upon with either the Investigator or the study monitor.

The handling of data, including data quality assurance, will comply with regulatory guidelines (e.g., ICH and GCP) and the sponsor's or its designee's SOPs and working instructions. Data management and control processes specific to this study will be described in a data management plan. When data management is outsourced, the contract organization will be responsible for the development and implementation of the data management plan.

Data Quality Assurance: All data on the CRF will be entered into a validated database compliant with 21 CFR Part 11 requirements. In the case when data management is outsourced, the contract organization will be responsible for database quality assurance including, but not limited to, review of data entered into the CRFs by study center personnel for completeness and accuracy and instruction of the study personnel to make any required corrections.

Data management at Indiana University will implement edit checks on the eCRF to enforce data integrity and compliance to the protocol and regulatory requirements. Study center personnel will be responsible for entering study data on the eCRFs. Data management will track eCRFs and review them for completeness, the presence of mandatory values, consistency, and dated electronic signatures. Queries identified during data discrepancy review will be sent to the study center personnel to be reviewed and resolved in a timely manner.

Adverse Events will be coded using the MedDRA dictionary. Concomitant medications will be coded using the WHO Drug dictionary. Adverse Events and Concomitant Medications will be reviewed for coding consistency and completeness.

At the end of the study, the database will be locked and the data will be released for reporting and statistical analysis.

13 ETHICS/PROTECTION OF HUMAN SUBJECTS

13.1 ETHICAL STANDARD

The Investigator(s) will conduct the study in accordance with this protocol, the guiding principles of the Declaration of Helsinki, ICH GCP guidelines and applicable regulatory requirements.

13.2 INSTITUTIONAL REVIEW BOARD

Before this study starts, the protocol will be submitted to each IEC/IRB for review. As required, the study will not start at a given center before the IEC/IRB for the center provides written approval or a favorable opinion. The IRB will meet all FDA requirements governing IRBs (Code of Federal Regulations, Title 21, Part 56). The IEC will meet local regulations.

13.3 INFORMED CONSENT PROCESS

13.3.1 CONSENT/ASSENT AND OTHER INFORMATIONAL DOCUMENTS PROVIDED TO PARTICIPANTS

Each patient must be provided with a statement that the investigation involves research and that the IRB/EC has approved solicitation of patients to participate; a fair explanation of the procedures to be followed and their purposes, including identification of any procedures which are experimental; a description in lay language of any possible side effects; a description of any attendant discomforts and risks reasonably to be expected; a description of any benefits reasonably to be expected; a disclosure of any appropriate alternative procedures that might be advantageous for the patient; an offer to answer any inquiries concerning the procedures, and instruction that the person is free to withdraw consent and discontinue participation in the project or activity at any time without prejudice to the patient. The informed consent shall include a disclosure that the Investigator is being supported by the NIH to perform the stated research.

13.3.2 CONSENT PROCEDURES AND DOCUMENTATION

A properly executed, written consent in compliance with current U.S. federal code 21CFR part 50, or competent regulatory authority, shall be obtained from each patient prior to entering the study or prior to performing any unusual or non-routine procedure involving risk to the patient.

A patient must give written consent to participate in the study. This consent must be dated and retained by the Principal Investigator as part of the study records. A copy shall be given to the patient. The informed consent process must be documented in the patient's source documents.

Written and/or oral information about the study in a language understandable by the patient will be given to all patients.

13.4 PARTICIPANT AND DATA CONFIDENTIALITY

Each Investigator must assure that the privacy and confidentiality of each study patient's, personal identity and personal medical information is, maintained at all times. In order to maintain subject privacy and confidentiality, all CRFs, laboratory specimens, evaluation forms, reports, and other records, documents and image material that leave the site will be identified only by an identification code. This identification code shall on no occasion include study subject's names, initials or date of birth.

Personal medical information may release or review the personal health data of study patients shall take place solely within circumstance, and to third parties, specifically identified by the written informed consent document signed by the study patients, except as permitted by applicable laws and regulations for purposes of monitoring and data verification by the relevant regulatory authorities, the NIH and NIH's properly authorized representatives, the quality assurance unit, or regulatory authorities. Personal medical information will always be treated as confidential.

14 DATA HANDLING AND RECORD KEEPING

14.1 DATA COLLECTION AND MANAGEMENT RESPONSIBILITIES

Each Investigator must keep a separate patient identification list showing code numbers, names, and dates of birth to allow unambiguous identification of each patient included in the study. A note will be made in the medical records that the patient is participating in a clinical study.

All required data will be recorded on the CRF by study center personnel according to the data entry guidelines provided by the PI or designee. All CRFs must be kept in good order and updated so they always reflect the latest observations on the patients participating in the study.

When paper CRFs are used, they will be completed legibly in black ink, with reasons given for missing data. Any corrections to the data will be made in a manner that does not obscure the original entry and will be dated and initialed by the Investigator or assigned designee. Each Investigator will sign the statement on the last page of the CRF.

When eCRFs are used, electronic signatures of the Investigator (or designee) will be provided.

Access to the eCRF for data entry and signature is controlled by user identification and password, which are provided by the PI or designee. Study center personnel will be trained, by the PI or designee, in the use of eCRFs and application of electronic signatures before the start of the study.

Because it is extremely important to have proper data collection in a timely manner, the Investigator shall complete the CRFs and on an ongoing basis. If a study monitor is needed and study monitor requests additional data or clarification of data for the CRF, the request must be answered satisfactorily in a timely manner before the next monitoring visit.

